Service Dog Training Program for Military Veterans With PTSD

NCT03777020

05-30-2023

Protocol

This RCT will gather data from 60 veterans with Post-traumatic stress disorder (PTSD) and 30 service dogs (SDs) in training. Veterans will be recruited and screened for eligibility according to Warrior Canine Connection (WCC) inclusion criteria Humans: 1) military veteran; 2) diagnosis of PTSD; 3) able to give informed consent; and 4) able to understand English. Human Exclusion Criteria: 1) fear of dogs; 2) allergy to pet dander; 3) active substance abuse; 4) active psychosis, or 5) history of animal abuse. Dog Inclusion Criteria: 1) non-aggressive demeanor as evaluated by WCC protocols for evaluating animal temperament; 2) cleared by veterinarian; and 3) up-to date immunizations. Dog Exclusion Criteria: 1) medical holds.

Recruitment/Screening: Recruitment will be via media attention, flyers, social media, and word of mouth.

Procedures: Veterans interested in the participating in the study will be prescreened by a research team member(RTM) for eligibility. Eligible veterans will be invited to participate. If veterans agree to participate after their questions are answered. They will be consented verbally, randomized, and scheduled for their first session with the location dependent on the arm. After informed consent is signed, baseline data will be obtained in an outdoor area at WCC [service dog training program(SDTP) arm] or at another meeting place near the participant's home [wait list control intervention((WLCI) arm)].

Randomization: Participants will be block randomized, according to gender, into the SDTP or WLCI. Group assignments will be generated by a computerized random number table and envelopes will be opened after verbal informed consent. Participants will continue existing therapies and begin any for which they are referred while in the study.

Interventions:

SDTP-Intervention (human): Veterans randomized to the SDTP will be paired with an experienced WCC Mission Based Trauma Recovery (MBTR)-Trainer (MBRT-T) and a SD. One hour training modules will be scheduled once a week for 8 weeks. Participants will come to WCC for all the weekly training modules. The MBTR-T will deliver the prescribed SDTP modules created by WCC. Each session will be fully supervised by a WCC MBTR-T to address any concerns or safety issues that may arise.

Waitlist Control Intervention (WLCI): Veterans randomized to WLCI will participate in one hour online SD training modules (<https://e-trainingfordogs.com>) scheduled once a week for 8 weeks but not interact with service dogs. The online training modules are delivered by experienced SD trainers and will employ parallel content to the WCC SDTP. Participants will participate from their homes or at a location of their choice in online training modules.

Outcome Assessment: In both groups, human's biological [e.g. salivary and heart rate variability (HRV)] markers except telomere length (TL) will be assessed in weeks 1, 4, and 8. TL will be assessed at weeks 1 and 8. Scales for and psychosocial data will be completed prior to session 1 and after sessions 4 and 8. HRV will be recorded in the human participants during SDTP sessions and for 30 minutes after sessions.

Assessment: Human Demographics and Characteristics Questionnaire will collect demographic/descriptive data on the human participants, such as gender, age, race, ethnicity, marital status, educational level, living arrangements, military history and pet ownership history. The order of the questionnaires will be randomized to minimize order effects. A dog demographics and characteristics questionnaire will collect demographic/descriptive data including dog's name, WCC dog trainer's name, gender, age, breed, and weight. Additionally, a photo will be taken to illustrate size and face.

Aim 1 Outcome Assessment:

Primary outcome: PTSDSS will be assessed with the PTSD Checklist for DSM-5 (PCL-5), a 20-item scale.^{70,71}

Secondary outcomes:

a) Stress markers will be assessed with salivary cortisol, α - amylase, and HRV, and the perceived stress scale. Heart rate variability (HRV) of veterans will be measured with a Polar H7 heart rate sensor worn around the chest and matching Polar V800 GPS Sports Watch worn around a wrist to save data from the heart rate sensor and download it for analysis. Perceived stress (PS) will be assessed with the Patient-Reported Outcomes Measurement Information System (PROMIS) Perceived Stress Fixed Form v2.0 (PROMIS, PS).^{72,73} and

b) Psychosocial health related to PTSD will be assessed with well validated scales, including PROMIS measures: Positive Affect-Short Form 15 (PA 15a),⁷⁵ PROMIS Satisfaction with Social Roles and Activities (SSRA) – Short Form 4a (PROMIS-SSRA),^{80,81} PROMIS Short Form v1.0- Satisfaction with Participation in Discretionary Social Activities- Short Form 7a (PROMIS SPDSA),^{82,83} PROMIS Companionship – Short Form 4a (PROMIS-C),^{84,85} PROMIS Depression Short-Form 8a,⁸⁷ and the PROMIS Anxiety Short-Form 8a.⁸⁸ Suicide ideation (SI) will be assessed with the Beck Scale for Suicide Ideation.⁸⁹ Quality of life will be assessed with the Veterans RAND 12-Item Healthy Survey,⁷⁶ Resilience will be assessed with the Connor-Davidson Resilience Scale (CD-RISC-10),⁷⁸ and Quality of an individual's relationships will be assessed with the Relationship Scale Questionnaire (RSQ).⁷⁹

c) The exploratory outcome: cellular aging will be assessed by obtaining absolute telomere length analysis.⁹⁰

Aim 2 Outcome Assessment: Dog HRV, is a reliable measure of stress levels.^{59,91} will be measured with the PetPace Collar (<http://petpace.com>). This non-invasive, monitor wirelessly tracks the dog's HRV and a range of physical and behavioral parameters.

Aim 3 Outcome Assessment: Participant attendance and participation in each session will be recorded by the SD trainers. The SD trainers also keep extensive notes on the interactions between the veterans and the dogs. Documentation of unintended consequences such as aggressive behavior (on either part), allergic reactions, fearful behavior (on either part). These logs will be used to assess participation in the SDTP. Exit phone interviews will be used to obtain veterans' perceptions of the SDTP and their outcomes.

Data Analysis Plan

Human Data: Before analyses, data will be cleaned and illustrated graphically. Summary statistics will be calculated, assumptions examined, and transformations applied as needed. Demographics and baseline characteristics (e.g., PTSDSS, gender) will be compared between the SDTP and WLCI groups, and the relevant variables considered as covariates for multivariable longitudinal analyses. SPSS 25 will be used for all analyses. Significance for rejecting the null is set at $p \leq .05$, Bonferroni sequential corrections will be used for multiple comparisons. The intent-to-treat approach will guide hypothesis testing. Separate sets of analyses are conducted for each outcome.

H1: Participants in the SDTP ($n = 30$) will demonstrate significantly greater improvement in outcomes from week 1 to weeks 4 and 8 than the WLCI ($n = 30$) in: a) PTSD symptom severity; b) stress markers (decreased cortisol, α -amylase, perceived stress; increased IgA, HRV); c) psychosocial health (increased positive affect, QOL, resilience, and relationships with friends and family, satisfaction with social activities and roles, companionship and decreased depression, anxiety, and suicide ideation); and d) exploratory stress marker cellular aging [increased TL, from weeks 1 to 8 only].

Linear mixed models (LMMs) with random intercepts (participant as a random variable) will be used to assess differences in changes in each outcome between the SDTP and WLCI participants, accounting for the correlation with the repeated measurements of each participant, and using all available data. Fixed effects will include group (SDTP or WLCI), week (1, 4 and 8), and their interaction, as well as the relevant covariates. The hypothesized effect of the intervention will be tested with the week by group interaction. Interactions of covariates (e.g. gender and age) with the group and time will be explored to provide information about their influence and for preliminary data to justify formal evaluation (with adequate power) in future studies. The multi-modal assessment in this study will provide the opportunity to explore characteristics that predict benefits.

Dog data: For analyses of data from dogs, demographics and baseline characteristics (e.g., size, gender, age), will be computed. The distributional characteristics of HRV (e.g., normality, outliers and missing) will be explored. Appropriate steps will be used as needed to ensure that applicable assumptions are met. Descriptive statistics will be computed for HRV by week and period (pre, during, and post).

H2: Dogs who participate in the SDTP will not experience increases in stress (decreases in HRV) from the 30 minutes before, to during, and after SDTP sessions. LMMs with random intercepts (dog as a random variable)

will be used to assess the significance of changes between the three periods, accounting for the correlation within the repeated measurements. Fixed effects will include period [pre, during, post SDTP session] and week (1, 4, 8). The hypothesized effect of the SDTP will be tested by evaluating the contribution of period to HRV. Interactions of dog covariates (e.g., dog gender and age) with period will be explored to evaluate their potential influence and for exploring a need for evaluation of their roles.

H3: Dogs who participate in the SDTP will not experience increases in stress (decreases in HRV) over 8 weeks of the SDTP. The hypothesized effect of the intervention will be tested by evaluating contribution of week to HRV based on the LMM used for aim 2. Interactions of dog covariates (e.g. gender, age) with week will be explored to provide information about their potential influence to inform development of future studies.

Feasibility data: Descriptive statistics will be calculated for number of sessions attended, rates of completion, drop out adverse events, and follow up questions, etc. Effect size estimates will be calculated for each veteran outcome and for dog HRV. They will enhance sample size calculations for a future multi-program RTC.

Missing Data. While complete data are ideal and we will make considerable effort to obtain them, some missingness is likely. Randomness of missingness will be tested. If there is excessive or differential attrition across groups or informative missingness, we will apply sensitivity analysis, such as pattern mixture models for longitudinal data.⁹² If the results differ, we will report both.

References

2. Bureau USC. FFF: Veterans Day 2017: Nov. 11. 2017.

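### Allocation is revealed after verbal consent but, on the natural reading, before signed consent and any baseline measurement, so veterans lost in between are randomised without data and the intent-to-treat comparison is open to arm-related selection.

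*Combined protocol and SAP*

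**What the plan says.** The Procedures paragraph gives the entry sequence: prescreening, an invitation, and then "They will be consented verbally, randomized, and scheduled for their first session with the location dependent on the arm". The next sentence begins "After informed consent is signed, baseline data will be obtained in an outdoor area at WCC" for the service dog training arm (SDTP). For the online waitlist arm (WLCI) it gives a meeting place near the participant's home. The Randomization paragraph repeats the trigger for disclosure: "envelopes will be opened after verbal informed consent". It also gives the method: "Participants will be block randomized, according to gender, into the SDTP or WLCI".

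On the analysis side, the Human Data paragraph of the Data Analysis Plan states: "The intent-to-treat approach will guide hypothesis testing". No analysis set is defined. Under H1 the primary model is a random-intercept linear mixed model, "accounting for the correlation with the repeated measurements of each participant, and using all available data". The sample is described by the data it yields: "This RCT will gather data from 60 veterans with Post-traumatic stress disorder (PTSD) and 30 service dogs (SDs) in training", with 30 veterans per arm under H1. The number to be randomised is not stated separately.

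The Missing Data paragraph provides for sensitivity analysis, with pattern mixture models as the example, if attrition is excessive or differs between arms, or if missingness is informative. The Feasibility data paragraph lists completion and dropout as descriptive statistics. Neither mentions veterans who are allocated but never sign or never start.

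**The concern.** Signing and attending the first session are decisions made after allocation, with the arm known. The arms differ in both appeal and burden. Veterans are recruited to a service dog study. One arm works with a dog and travels to the training site weekly for 8 weeks. The other takes online modules and has no contact with service dogs. A veteran who hoped for a dog may withdraw from the online arm, and one who finds the travel hard may withdraw from the dog arm.

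Such a veteran has been randomised, yet leaves no PCL-5 score or other study measurement. What is then compared is veterans who accepted their arm, not veterans as randomised. The planned comparison of baseline characteristics would not show the loss, because it also covers only those who signed and were measured. If the target of 60 counts veterans with data, those lost could be replaced and the final count would look complete.

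**Working it through.** **Order of events.** Put side by side, the two paragraphs give:

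1. Prescreening for eligibility.
2. Verbal consent.
3. Envelope opened.
4. First session scheduled at a place that depends on the arm.
5. Consent signed.
6. Baseline data collected at that place.

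Steps 2 to 4 are explicit, and so is 5 before 6. That 5 follows 3 is the natural reading. The text does not say it outright, but it makes only verbal consent a condition of opening the envelope, and it introduces the signature after scheduling.

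**What the model can use.** A mixed model on all available data uses a participant's records at weeks 1, 4 and 8. With none, the participant contributes nothing. A pattern mixture model could bring such veterans in only through assumptions made outside the data, and the plan specifies none.

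**Size, for illustration.** The documents give no refusal rate, SD, effect size or power calculation, so there is no figure of the plan's own to reproduce. Inputs:

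- 30 randomised per arm (H1).
- Two-sided 5% test. The 5% is in the Human Data paragraph; two-sided is assumed.
- f = share of an arm lost before baseline (assumed).
- D = difference in expected PCL-5 change between those lost and those kept, in SD of change (assumed).

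If those kept have mean change m, the whole randomised arm has mean (1 − f)m + f(m + D) = m + fD. The analysed mean is m, so that arm is off by f × D. The net bias is the difference between the two arms' values of f × D.

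The rejection rate with no true effect is taken from a two-sample t-test on change (noncentral t), a simplification of the planned week-by-group test. The standard error in SD units is √(1/n₁ + 1/n₂), and the noncentrality is bias divided by standard error.

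| Lost, arm A v arm B | D (SD) | n analysed | Bias (SD) | Rejection rate |
|---|---|---|---|---|
| 0% v 10% | 0.5 | 30 v 27 | 0.05 | 5.4% |
| 0% v 10% | 1.0 | 30 v 27 | 0.10 | 6.6% |
| 0% v 20% | 0.5 | 30 v 24 | 0.10 | 6.5% |
| 0% v 20% | 1.0 | 30 v 24 | 0.20 | 11.1% |
| 10% v 20% | 0.5 in both | 27 v 24 | 0.05 | about 5.4% |
| 10% v 20% | 1.0 in both | 27 v 24 | 0.10 | 6.4% |
| 10% v 10% | equal | 27 v 27 | 0 | 5.0% |

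For the fourth row, the standard error is √(1/30 + 1/24) = 0.274 and the noncentrality is 0.20/0.274 = 0.73, which gives 11.1%. A normal approximation gives 11.3%.

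Equal shares remove the bias only if the gaps are also equal. With 10% lost in each arm and gaps of +0.5 and −0.5 SD, the net bias is 0.10 × 0.5 + 0.10 × 0.5 = 0.10 SD.

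**The case against.** The strongest reply is that the harm is conditional. If everyone signs and attends, nothing is lost. The rejection rate stays near 5% over much of the assumed range, and motives to withdraw exist in both arms, so losses may partly cancel. All of this stands. A reader might go further and infer that randomisation no longer protects the PCL-5 comparison. The documents do not support that: they show an opening for selection, not that selection occurs or how large it is. A rate near 18% can be reached by assuming 30% lost from one arm only and a gap of 1.0 SD, but nothing in the documents points to those values.

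A reader might also infer that the loss could never be detected. That is too strong. Each opened envelope is a recorded allocation and gender is known from the blocking, so those lost can be counted by arm. The plan already intends to describe dropout and to react to differential attrition. What remains is that it does not name this group or ask for the count, and a count alone does not supply their outcomes.

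A third reply is that moving only the signature ahead of the envelope would not cure the problem. A veteran who signs, learns the arm and stays away still has no baseline. This is correct, and it is why the remedy must move a baseline measurement as well.

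Finally, the consent pages are not in the public text, so the scope of verbal consent cannot be seen. That bears on what may be reported about those who never sign. It does not change the order of events.

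**Conclusion.** The point holds as a weakness of sequence and definition. Allocation is disclosed on verbal consent and, on the natural reading, before signature and before any study measurement. Veterans lost in that interval cannot enter the planned analysis, and the plan does not say how they are counted or reported.

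The bias of 0.05 to 0.20 SD, with a rejection rate of about 5.4% to 11%, rests on assumed losses of 10% to 20% in one arm only and an assumed gap of 0.5 to 1.0 SD. The direction cannot be known from the documents, and the net effect is smaller where similar losses occur in both arms. The sequence should be fixed because it bears on the primary comparison and costs little to change. The documents do not show that the trial's result would be invalid without the change.

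**What to change.** In Procedures and Randomization, change the order to: eligibility confirmed, consent signed on paper or electronically, baseline self-report scales including the PCL-5 completed, then envelope opened. Everyone randomised then has a baseline record. Biological baseline samples may stay at the first session. A veteran who declines to sign is then never randomised. One who withdraws after allocation becomes ordinary dropout: the follow-up is still missing, but the loss is visible and the baseline score is there to model it with.

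In the Data Analysis Plan, define the intent-to-treat set as every veteran whose envelope was opened. State whether the 60 counts veterans randomised or veterans with data, and do not replace non-starters without record. Report withdrawals between allocation and session 1 by arm. If veterans have already entered under the present order, the definition and the by-arm report can still be applied to them.

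The cost is protocol wording and a small logistical change: consent and questionnaires move to the screening contact or are done remotely. The scales are already due before session 1, so no assessment is added.

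### The week-1 PCL-5 and other self-report scales are completed after allocation is revealed and at an arm-specific place, so any reaction that fades enters the week-by-group test of H1

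*Combined protocol and SAP*

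**What the plan says.** **Order of events.** Procedures: "They will be consented verbally, randomized, and scheduled for their first session with the location dependent on the arm". Randomization: "envelopes will be opened after verbal informed consent". Baseline follows as a separate, later step, after written consent: "baseline data will be obtained in an outdoor area at WCC [service dog training program(SDTP) arm] or at another meeting place". The second of these places is for WLCI and lies close to where the veteran lives.

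**Timing of the scales.** Outcome Assessment: "psychosocial data will be completed prior to session 1 and after sessions 4 and 8". The first completion therefore belongs to this post-allocation baseline.

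**Use in the analysis.** Under H1 in the Data Analysis Plan, "Fixed effects will include group (SDTP or WLCI), week (1, 4 and 8), and their interaction", and "The hypothesized effect of the intervention will be tested with the week by group interaction". The Human Data paragraph adds a check: "Demographics and baseline characteristics (e.g., PTSDSS, gender) will be compared between the SDTP and WLCI groups", with relevant variables considered as covariates.

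The documents describe no measurement before allocation, no common baseline setting and no masking of veterans.

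**The concern.** A baseline taken before allocation cannot differ between arms except by chance. Here the week-1 self-reports can differ for two further reasons: the veteran knows the assignment, and the place of completion depends on it. The plan does not say in words that the veteran is told the arm. However, a veteran already scheduled to an arm-specific place can hardly be unaware of it.

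Because week 1 is one of the three outcome levels in the tested interaction, a reaction present then and gone by weeks 4 and 8 is counted as differential change. If SDTP scores are lowered at week 1, a real benefit is partly hidden. If they are raised, false findings of benefit become more frequent. The documents do not favour either direction.

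The point is limited to the self-report scales. The plan gives no pre-session timing for the salivary markers, and it ties veteran HRV to the sessions.

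**Working it through.** The plan states no power, SD, within-person correlation or expected shift for H1, so there is no figure of its own to reproduce. What follows is an illustration.

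**Inputs from the plan:** 30 veterans per arm; weeks 1, 4 and 8; random-intercept model; significance level 0.05.

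**Assumptions:** within-person correlation ρ of 0.5, 0.6 or 0.7; outcome SD of 1; no dropout, covariates or multiplicity correction; a shift of *b* SD in one arm at week 1.

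**Step 1: what enters the test.** Let the arm difference be *b* at week 1 and *pb* at weeks 4 and 8, where *p* is the part that persists. The difference in change is then −*b*(1 − *p*). With *p* = 1 it is zero; with *p* = 0 it is −*b*.

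**Step 2: rejection rate with no true effect.** The interaction F test has 2 and 2 × (60 − 2) = 116 df. Its noncentrality is the sum of squared centred arm differences divided by (2/30)(1 − ρ). For a week-1-only shift the sum is (2/3)*b*², so the noncentrality is 10*b*²/(1 − ρ). Example: *b* = 0.2 and ρ = 0.5 give 10 × 0.04/0.5 = 0.8, and a rejection rate of 11.3%.

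| Shift, no true effect | ρ = 0.5 | ρ = 0.6 | ρ = 0.7 |
|---|---|---|---|
| 0.1 SD, week 1 only (or 0.2 SD, half persisting) | 6.5% | 6.9% | 7.5% |
| 0.2 SD, a quarter persisting | 8.5% | 9.4% | 10.9% |
| 0.2 SD, week 1 only | 11.3% | 13.0% | 16.0% |
| Any shift, fully constant | 5.0% | 5.0% | 5.0% |

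The plan applies a sequential Bonferroni correction without giving the number of comparisons. At a 2.5% level, for example, the week-1-only rates are 3.4%–4.1% (0.1 SD) and 6.6%–9.9% (0.2 SD).

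**Step 3: direction.** This was simulated with 40,000 trials per setting and no true effect, taking direction from the mean of weeks 4 and 8 minus week 1. The nominal rate of significant results favouring SDTP is 2.5%.

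- SDTP week 1 raised: 5.3%–6.7% favour SDTP (0.1 SD) and 10.9%–15.3% (0.2 SD).
- SDTP week 1 lowered: 0.9%–1.1% favour SDTP (0.1 SD) and 0.3%–0.4% (0.2 SD).

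**Step 4: power for a true 0.5 SD benefit at weeks 4 and 8.**

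| SDTP week 1 | ρ = 0.5 | ρ = 0.6 | ρ = 0.7 |
|---|---|---|---|
| No shift | 49.3% | 59.1% | 72.4% |
| Lowered 0.1 SD (or 0.2 SD, half persisting) | 33.3% | 40.6% | 52.0% |
| Lowered 0.2 SD | 20.2% | 24.4% | 31.4% |

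**Step 5: do the planned safeguards help?** A two-sample baseline t test (58 df) flags a 0.1 SD shift 6.7% of the time and a 0.2 SD shift 11.9% of the time, so it would usually miss either. Adjusting week 8 for the shifted baseline leaves a bias of ρ*b*: 0.05–0.07 SD for a 0.1 SD shift (rejection 5.6%–6.6%) and 0.10–0.14 SD for a 0.2 SD shift (7.2%–11.6%). That shrinks the problem without removing it.

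**The case against.** The sequence is not in dispute; the weight given to it is.

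- **No evidence of a reaction.** The documents show neither its size nor its direction, and every percentage depends on an assumed shift that must also fade. A 0.2 SD shift of which three-quarters persists gives only 5.4%–5.6%. This stands: certainty attaches to the order of events, not to the amount of harm.
- **Place may cancel.** SDTP veterans attend WCC for every session, so a pure place effect in that arm may be constant. This stands in part. WLCI veterans give baseline at a meeting place but take the modules at home or wherever they choose, and the plan does not say where the week 4 and 8 scales are completed. Knowledge of the arm remains as a cause in either case.
- **Reordering opens another exposure.** A reporting difference constant since allocation cancels now. With a pre-allocation baseline it would appear at weeks 4 and 8 only, with the same noncentrality: 6.5%–7.5% for 0.1 SD and 11.3%–16.0% for 0.2 SD. This stands as a limit. It arises because self-report is unmasked, which no ordering cures. It does not justify leaving the baseline itself open to the influence of allocation.
- **Pilot purpose.** The effect sizes are meant to inform a later trial. That does not lessen the point, because a distorted week 1 would distort those estimates too.

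**Conclusion.** The concern holds. The plan places the first self-reports after allocation and in arm-specific settings, then uses them as one of the three outcome levels in the primary test, and no planned step removes a resulting shift. It is a risk of bias of unknown direction. Under the stated assumptions, a reaction of 0.1 to 0.2 SD confined to week 1 would raise the overall false-positive rate from 5% to between 6.5% and 16.0%. If it lowered SDTP scores, power for a 0.5 SD benefit would fall from 49%–72% to between 20% and 52%. A reaction that persists in full has no effect on the test. The plan should be changed, because the remedy is conventional and cheap.

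**What to change.** **If baselines are still to be collected:** obtain signed consent; have every veteran complete the PCL-5 and the other self-report scales under the same conditions; then open the envelope and schedule session 1. Session-linked HRV can stay as planned. State that this does not mask the later self-reports, and that an arm difference constant since allocation would then count as part of the effect of assignment. The cost is one earlier contact per veteran, and a few veterans with baseline data who are never randomized.

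**If data are already collected:** disclose the order. Report by arm the envelopes opened, consents signed and baselines completed; this also shows any loss between allocation and baseline. Add a sensitivity comparison of the mean of weeks 4 and 8 that does not use week 1. Its standard error is √[(2/30)(1 + ρ)/2], which is 0.224, 0.231 and 0.238 SD for ρ = 0.5, 0.6 and 0.7. Its power for 0.5 SD is 59.4%, 56.7% and 54.2%, against 49.3%, 59.1% and 72.4% for the unshifted interaction, so it gains at low correlation and loses at high correlation. State beside it that a constant arm difference does not cancel: 0.2 SD gives 13.1%–14.2% rejection with no true effect. The cost is one flow table and one extra analysis.

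### The PCL-5 and other scales are scheduled by session attended but analysed by week under intent-to-treat, so follow-up is undefined for veterans who miss sessions or stop attending

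*Combined protocol and SAP*

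**What the plan says.** All references are to the combined protocol and SAP.

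- **Outcome Assessment**, on the scales: "Scales for and psychosocial data will be completed prior to session 1 and after sessions 4 and 8". The sentence is garbled, but the Aim 1 section describes the PCL-5 as a scale and gives it no other schedule, so this is the only timing rule for the primary outcome.
- **Outcome Assessment**, same paragraph, on the biological measures: "markers except telomere length (TL) will be assessed in weeks 1, 4, and 8".
- **Interventions**, SDTP arm: "One hour training modules will be scheduled once a week for 8 weeks". The WLCI modules are likewise "scheduled once a week for 8 weeks but not interact with service dogs".
- **Data Analysis Plan, Human Data**: "The intent-to-treat approach will guide hypothesis testing".
- **Data Analysis Plan, H1**: SDTP participants "will demonstrate significantly greater improvement in outcomes from week 1 to weeks 4 and 8 than the WLCI". On the model: "Fixed effects will include group (SDTP or WLCI), week (1, 4 and 8), and their interaction, as well as the relevant covariates". On the test: "The hypothesized effect of the intervention will be tested with the week by group interaction". The model keeps whatever data each participant has supplied.
- **Missing Data**: some missing values are expected and an effort to avoid them is promised. Sensitivity analysis, with pattern mixture models as the example, follows if attrition is excessive, differs by arm or is informative.

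The document gives no assessment window, no rule on whether a missed session is skipped or made up, no rule for assigning an off-schedule score to a week, and no procedure for obtaining the PCL-5 from a veteran who has stopped attending.

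**The concern.** The primary outcome is triggered by a treatment event, while the hypothesis and the model are framed in time since the start. An intent-to-treat comparison needs follow-up on everyone randomised, whether or not they kept to the programme. Followed literally, the schedule never reaches its trigger for a veteran who leaves after session 3. That veteran stays in the model through the baseline score but supplies no observed change.

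The plan foresees imperfect attendance: the Feasibility data paragraph will report sessions attended, completion and dropout. What is at stake is the week-by-group contrast on PCL-5 in a trial with 30 veterans per arm, and the meaning of week 8 for anyone who falls behind. Participants may also start newly referred therapies during the study, so a later reading allows more time for those to act.

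**Working it through.** **No stated figure to reproduce.** The document gives no power calculation, effect size, SD or expected dropout. The arm sizes in H1 agree with the total: 30 + 30 = 60. Everything below that uses a loss rate or a gap is an assumption.

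**1. When session and week agree.** Take session 1 as day 0. With weekly sessions, session k falls in week k, on day 7 × (k − 1).
- Session 4: 7 × 3 = day 21, in week 4.
- Session 8: 7 × 7 = day 49, in week 8.

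With no missed session the mismatch is zero.

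**2. If m sessions are missed and made up (assumption).** Session 8 moves to week 8 + m, on day 49 + 7m.

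| m | Session 8 in week | Day | Increase over 49 days |
|---|---|---|---|
| 1 | 9 | 56 | 7/49 = 14% |
| 2 | 10 | 63 | 14/49 = 29% |
| 3 | 11 | 70 | 21/49 = 43% |

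The model has only week 8 to hold any of these. If missed sessions are simply skipped, there is no lateness.

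**3. What remains after stopping, under the literal rule.**
- Stops before session 4: baseline only.
- Stops between sessions 4 and 8: baseline and the session 4 score.
- Completes session 8: all three.

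**4. Bias in the group contrast, as a worst case in which the model recovers nothing.** Let q be the share of an arm without the final score, and g the amount in SD by which attenders improve more than stoppers. The arm's true mean is (1 − q) × attenders + q × stoppers, so the attenders' mean exceeds it by q × g. With the same g in both arms, the contrast is biased by (q in SDTP − q in WLCI) × g.

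| Loss SDTP | Loss WLCI | g = 0.5 | g = 1.0 |
|---|---|---|---|
| 20% | 10% | 0.05 SD | 0.10 SD |
| 30% | 10% | 0.10 SD | 0.20 SD |
| 30% | 30% | 0 | 0 |
| 10% | 30% | −0.10 SD | −0.20 SD |

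**5. Precision, even where the bias cancels.** Assume a two-sided alpha of 0.05 (the plan does not state sidedness) and a simple comparison of two means. The detectable difference at 80% power is d = (1.96 + 0.84) × √(2/n).

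| Loss in each arm | n per arm | Detectable d | Power at d = 0.72 |
|---|---|---|---|
| 0% | 30 | 0.72 | 80% |
| 10% | 27 | 0.76 | 75.7% |
| 20% | 24 | 0.81 | 70.7% |
| 30% | 21 | 0.87 | 65.0% |

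The mixed model recovers some information from partial data, so these figures overstate the loss.

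**6. Whether the planned safeguards close the gap.** A promise of effort does not say who is assessed after stopping, or when. The mixed model lets others in the same arm stand in for a baseline-only veteran. A pattern mixture model has no follow-up data in the baseline-only pattern, so the change there must be assumed. The exit phone interviews cover perceptions of the programme and outcomes, but are not described as a PCL-5 assessment.

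**The case against.** The best defence is that session and week are used interchangeably for a weekly programme. Human HRV supports this: it is among the markers set by week, yet it is recorded during and after SDTP sessions. The mixed model is not a completers' analysis, the Missing Data paragraph names differential attrition explicitly, and it commits to reporting both results if they differ.

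Much of this stands, and it rules out several stronger readings that a reader might infer:

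- *Veterans who stop have no outcome.* The baseline score, and the session 4 score if reached, stay in the model. Nothing says the scales are withheld from those who stop.
- *Late scores will be coded as week 8.* This needs make-up sessions, which the document never mentions.
- *The SDTP result describes attenders only.* A likelihood model on partial data adjusts for loss so far as the observed scores predict it.
- *Loss will be greater in SDTP because those veterans travel to the training site.* This is conjecture. No attrition data are given, and veterans given online modules without a dog could equally disengage.
- *A loss in one arm carries straight into the treatment effect.* An attenders-versus-arm difference is a single-arm quantity. H1 tests the contrast, where equal loss with an equal gap cancels.

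The defence does not remove the literal rule. The only stated trigger for the primary outcome is completing a session, and no analysis can restore a score that was not collected.

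**Conclusion.** The concern holds in a limited form. The timing of the scales and the timing in the H1 model agree only for veterans who miss no session. For the rest, the plan schedules no follow-up after attendance stops and does not say how an off-schedule score is assigned to a week.

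The effect on the primary contrast cannot be computed from the document. Under assumed losses of 30% versus 10% and a gap of 0.5 to 1.0 SD it is about 0.10 to 0.20 SD if the model recovers nothing. It is smaller so far as earlier scores predict stopping, zero with equal loss and gap, and reversed if WLCI loses more. Its direction is therefore not known in advance. The change is worth making because it is cheap and because scores not collected at the time cannot be obtained later.

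**What to change.** 1. Schedule the scales at week 4 and week 8, counted in both arms from the scheduled first session. Every randomised veteran then has target dates.
2. Set a window that contains the on-schedule session, for example days 21-28 and 49-56 with the scheduled first session as day 0. Windows of three days either side of days 28 and 56 would not do: they run from 25 to 31 and from 53 to 59, and exclude the on-schedule days 21 and 49.
3. Seek the scales from every randomised veteran whether or not sessions were attended or completed, with the same remote option in both arms for those not attending.
4. Record the actual assessment date and the number of sessions attended by then.
5. Define week in the H1 model in this sense, and state how a score outside the window is handled.

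**Cost.** A wording change and reminder calls. Collection modes will be mixed to some extent, which is why the remote option should be identical in both arms. The battery includes the Beck Scale for Suicide Ideation, so remotely returned responses must be covered by the study's safety procedures. Some veterans will have had fewer than 8 sessions at the final reading, so the estimated effect may be somewhat smaller. That is the effect an intent-to-treat analysis is meant to estimate.
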